Remaining missing ordinal scores for subjects that terminated early from the study and were still hospitalized at the time of their last assessment or with discharge to a location of hospice, LTAC or other hospital at the time of last contact will be imputed using multiple imputation. A sensitivity analysis of this analysis will be

performed using multiple imputation for all subjects missing ordinal after their last assessment regardless of their discharge status at the last assessment. Details of multiple Imputation are provided in Section 6.5.2.

Some analyses of ordinal score such as those reported in Table 17, Table 18, Table 20, Table 21, Table 24, Table 25, Table 26, Table 27, Table 34, Table 35, Figure 4, Figure 5, Figure 6, Figure 7, and Figure 18 will be based on complete ordinal score data created using the following steps:

- If a subject is discharged from the hospital to a location other than LTAC, Hospice care or other hospital, has intermittent missing ordinal score and reported an ordinal score of 1 or 2 after the missing score then:
 - Impute the intermittent missing ordinal score as 1 if the scores reported before and after the missing value are both 1 and no change in oxygen use or hospitalization status after discharge to a location other than hospice, long term acute care or other hospital.
 - Impute the intermittent missing ordinal score as 2 after discharge to a location other than hospice, long term acute care or other hospital if the subject doesn't fall into the category above and subject is not hospitalized at the time point.
- LOCF will be used for remaining intermittent missingness of ordinal scores for the next planned assessment.
- All missing scores after death will be assigned an ordinal score of 8.
- Subjects discharged from the hospital to a location other than LTAC, hospice care or other hospital at their last assessment will be assigned a score of 2 for all timepoints after last assessment.
- Impute all remaining missing data after last assessment using last observation carried forward.

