6.5.2. Multiple Imputation

Multiple imputation will be performed for the primary endpoint of the Day 8 ordinal score for subjects whose last assessment in the study is before Day 8 and missing ordinal scores after their last assessment for the following two scenarios:

- For the primary analysis of the primary endpoint, assign a score of 2 for subjects missing Day 8 score after last assessment for subjects with a good discharge status (i.e., discharged to a location other than LTAC, hospice care, other hospital) at last assessment and use multiple imputation to impute missing data at Day 8 only for subjects without a good discharge status (i.e., subjects with no post baseline data or still hospitalized or those discharged to LTAC, hospice care, or other hospital) at their last assessment

- As a sensitivity analysis of the primary endpoint, use multiple imputation to impute missing ordinal scores for all subjects missing Day 8 ordinal scores after last assessment regardless of their good discharge status at last assessment.

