For analyses based on multiple imputation, remaining missing ordinal scores will be imputed for Day 8 using the PROC MI procedure in SAS. Treatment group (trtvar), baseline ordinal score (basesteroidusevar), baseline steroid use (basesteroidvar), duration of symptoms prior to randomization (dursymp), age, indicator for black or Hispanic ethnicity (blackhispl), presence of 2 or more comorbidities (comorb2fl), baseline CRP (basecrp), and indicator for discharge to a location other than long term care facility (LTAC), hospice care or another hospital (i.e., good discharge status) at the last assessment of the subject being imputed will be included as covariates in the multiple imputation model for ordinal scores at each timepoint using monotone logistic regression. The good discharge status variable at last assessment variable (goodischstat) will vary from subject to subject and will be defined as the discharge status for all subjects at the last assessed timepoint of the subject being imputed. For example, if the subject being imputed had their last assessment at Day 5, the good discharge status variable for all subjects will be defined as their discharge status at Day 5. The timing for the discharge status variable will be defined according to the last assessment timepoint of the subjects being imputed. The treatment group variable (trtvar) represents the randomized treatment group. Each imputation model will include all subjects with complete data plus all subject with missing ordinal score at Day 8 to be imputed who have the same last assessment day. The procedure will loop through all possible last assessment days (i.e., day 1 through day 8) imputing data for subjects missing data who were last assessed on the same day.

Since missing data in any of these baseline characteristics may cause issues with the monotone missing data patterns, the following methods will be used to fill in missing baseline covariates data:

- For continuous baseline covariates (age, CRP, duration of symptoms), mean imputation will be used to replace missing values with the overall mean value from all randomized subjects for the given covariate.
- For indicator variables of baseline steroid use, black or Hispanic ethnicity, and presence of two or more comorbidities, subjects with missing values will be given the value with the greatest number of subjects among all randomized subjects.
- We do not anticipate any missing data for actual baseline ordinal score.

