Twenty imputation sets will be generated, and final results from these 20 imputed datasets will be aggregated.

Pseudocode:

- Define `ordscore_d8` as the ordinal score:
- DEFINE `ordscore_d8` as the ordinal score value at Day 8.
- DEFINE `j`: as the last time assessment for the subjects being imputed used to define the good discharge status variable in the model. Possible values for `j` are from 1 to 8.
- DEFINE `jMax`= Maximum time of last assessment observed during the study.
- DEFINE `g&j`=analysis dataset containing predictors and ordinal score for complete data subjects as well as subjects missing Day 8 score who were last assessed on the same day.
- DEFINE `&&modelVars` = list of covariates to be used in the imputation model: `trtvar baseordscorevar basesteroidusevar dursymp age blackhispl comorb2fl basecrp goodischstat_j`.

- DEFINE imp_g&j = g&j with 20 imputed values for the missing ordinal score added by PROC MI.

```
%do j=1 %to &jMax;
```

```
proc mi data=g&j out= imp_g&j impute=20 seed = 300&j noprint;
  class trtvar baseordscorevar basesteroidusevar blackhispfl comorb2fl
  goodischstat_j ordscore_d8;
  var trtvar baseordscorevar basesteroidusevar dursymp age blackhispfl comorb2fl
  basecrp goodischstat_j ordscore_d8;
  monotone logistic(ordscore_d8 = trtvar baseordscorevar basesteroidusevar dursymp
  age blackhispfl comorb2fl basecrp goodischstat_j);
run;
  %end;
```

imp_g&j will be subset to contain only rows for the subjects with imputed ordinal scores and merged together with data from subjects with complete data to form twenty complete multiply imputed datasets. The final dataset imp_g will contain 20 replicates for complete subjects and data from the 20 imputation datasets for imputed subjects.

Proportional Odds analysis with multiple imputation:

The following SAS pseudocode will be used to perform the proportional odds analysis with treatment, baseline ordinal score and baseline steroid use as covariates to generate the treatment odds ratio, p-value, and predicted probabilities of the ordinal scale levels by treatment and ordinal score using data from multiple imputation:

```
proc logistic data=imp_g out=imp_parms plots(only)=effect(x= ordscore_d8
  sliceby =baseordscorevar*trtvar individual connect);
  by _imputation_;
  class baseordscorevar (param=ref ref=5) basesteroidusevar (param=ref ref=no
steroid use) trtvar (param=ref ref=placebolabel);
  model ordscore_d8 = trtvar baseordscorevar basesteroidusevar;
  oddsratio trtvar;

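### The imputation model for the primary Day 8 score leaves out the ordinal score at the last assessment, so inpatients lost at score 4 and at score 7 can get the same imputed distribution

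*SAP*

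**What the plan says.** SAP 6.5.1 fills some missing scores by rule before any multiple imputation. Scores after death become 8, good discharges with no later data become 2, and intermittent gaps are filled. What is left goes to multiple imputation: "Remaining missing ordinal scores for subjects that terminated early from the study and were still hospitalized at the time of their last assessment", together with those sent to hospice, long-term acute care or another hospital. SAP 6.5.2 repeats that the primary analysis will "use multiple imputation to impute missing data at Day 8 only for subjects without a good discharge status", and defines that group as "subjects with no post baseline data or still hospitalized or those discharged to LTAC, hospice care, or other hospital".

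The imputation is run once per last-assessment day j. The text of SAP 6.5.2 names the variables that "will be included as covariates in the multiple imputation model for ordinal scores at each timepoint using monotone logistic regression". The pseudocode in SAP 6.5.2 gives the "list of covariates to be used in the imputation model" as "trtvar baseordscorevar basesteroidusevar dursymp age blackhispl comorb2fl basecrp goodischstat_j", and the model statement begins "monotone logistic(ordscore_d8 = trtvar baseordscorevar basesteroidusevar dursymp" and continues through the same list. The only post-baseline entry is the good-discharge indicator on day j.

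The omitted score is collected. Protocol 8.1.2.1 and SAP 4.1 both have clinical status recorded every day in hospital.

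**The concern.** The subjects who reach this model after baseline are mostly inpatients who left the study before Day 8. For them the score on the last day seen is the obvious predictor of the Day 8 score, and it is on file. Leaving it out means that a patient last seen ventilated is imputed too favourably, and one last seen off oxygen but still in hospital too unfavourably.

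Missing at random then has to hold given baseline data alone, which is harder to defend than missing at random given status at loss. If the two arms lose subjects in different states, the errors do not cancel and the primary odds ratio moves. An arm is called promising at a two-sided p below 0.20, so a modest shift can matter.

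**Working it through.** **1. The plan's own figures.** The imputation section states no number to reproduce. As a check on scale, Table 5 was re-run at an odds ratio of 2 with Table 4 as the control distribution, both looks and 100,000 replicates. It gave power 0.762 (alpha 0.05) and 0.909 (alpha 0.20), futility 0.029 and interim efficacy 0.072; Table 5 has 0.765, 0.913, 0.028 and 0.070. The Whitehead formula alone gives 0.769 and 0.921. The planned power is sound and this point does not change it.

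**2. Structure.** Write x for treatment and the listed baseline covariates, g for good discharge on day j and s for the score on day j. The day-j model is

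logit P(Day 8 score ≤ k) = α(k,j) + x′β(j) + γ(j)·g.

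Every subject multiply imputed in the primary analysis has g = 0, and s does not appear. Equal x and equal j therefore give an identical imputed distribution for any s. The reference to each timepoint in the text does not bring s in, because only the Day 8 score is on the left of the model. At j = 1 the last score is the baseline score, so the gap concerns losses after baseline.

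**3. Illustration for one subject.** Assumed, not from the documents: half the subjects at baseline 5; a Day 5 distribution of 20% at score 2, 12% at 4, 28% at 5, 15% at 6, 23.5% at 7 and 1.5% dead; latent Day 5 to Day 8 correlation of 0.6, 0.8 or 0.9; baseline acting on Day 8 only through Day 5. Day 8 margins are from Table 4. A cumulative-logit model was fitted to those alive on Day 5 with baseline score, age and discharge status, then with the Day 5 score added. P(Day 8 score 7 or 8), undischarged, age 60:

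| Baseline | Correlation | SAP-type model, last score 4 or 7 | Score added, last 4 | Score added, last 7 |
|---|---|---|---|---|
| 5 | 0.6 | 0.269 | 0.111 | 0.577 |
| 5 | 0.8 | 0.236 | 0.045 | 0.677 |
| 5 | 0.9 | 0.221 | 0.012 | 0.779 |
| 6/7 | 0.6 | 0.359 | 0.112 | 0.580 |
| 6/7 | 0.8 | 0.401 | 0.049 | 0.700 |
| 6/7 | 0.9 | 0.421 | 0.014 | 0.805 |

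**4. Effect on the odds ratio.** Separate runs used assumed daily transition chains with no drug effect, all losses at score 7 in one arm and at 4–5 in the other. The odds ratio was 1.06 with 3% missing and 1.10–1.11 with 5%. Adding the last score returned 1.00, which a Markov chain guarantees.

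A hand check from step 3 agrees. Near the null, log OR ≈ 3D/(1 − Σp³), where D is the net probability that one arm does better. Table 4 gives Σp³ = 0.0625, so log OR ≈ 3.2D. Net ranks from Table 4 (probability of doing better minus worse than a random control) average 0.654 for score 2, −0.069 for 3–6 and −0.723 for 7–8. At correlation 0.8, P(score 2) in the same fits was as follows.

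- Lost at 7, baseline 6/7. SAP-type model (P(2) = 0.163): 0.163×0.654 − 0.436×0.069 − 0.401×0.723 = −0.213. Score added (P(2) = 0.028): 0.028×0.654 − 0.272×0.069 − 0.700×0.723 = −0.507. Error +0.293 before rounding.
- Lost at 4, baseline 5. SAP-type model (P(2) = 0.297): −0.009. Score added (P(2) = 0.592): 0.330. Error −0.338 before rounding.

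With a fraction m lost per arm, D = m(0.293 + 0.338) = 0.631m. For m = 3%, OR = exp(3.2×0.0189) = 1.06; for m = 5%, exp(3.2×0.0316) = 1.11. Correlations of 0.6 and 0.9 give 1.05 and 1.08 (3%), and 1.08 and 1.13 (5%). If both arms lose the same mix of subjects, the two errors are equal and D = 0 under the null.

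**5. Scale.** SE(log OR) at 100 per arm = √(12/(200×0.9375)) = 0.253. An odds ratio of 1.06 is 0.058/0.253 = 0.23 SE; 1.11 is 0.104/0.253 = 0.41 SE. Ignoring the interim look, the null chance of a promising result in the favoured direction rises from 0.10 to 1 − Φ(1.28 − 0.41) = 0.19 in the 5% case.

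**The case against.** The plan is not blind to the last score. Sensitivity Imputation 2 in Table 7 carries the last observation forward, and its result sits beside the primary one in Table 16. SAP 6.5.2 also plans a tipping-point analysis that varies Day 8 scores independently by arm. A reader might infer that nothing in the plan checks this; the documents do not support that.

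Few subjects should reach the model. Deaths and good discharges are fixed first, charts are reviewed for lost subjects, and an endpoint committee may adjudicate unclear discharges. SAP 6.5.1 expects little missing data. Administration and follow-up assessment are blinded (SAP 4.4.6), which makes sharply different loss patterns less likely. Losing only ventilated subjects in one arm and only recovering ones in the other is an extreme construction.

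All of that stands, and it limits the size. It does not repair the primary estimate. Carrying the score forward is a single fill with no further change or uncertainty, and only a sensitivity analysis. Sensitivity Imputation 1 adds good discharges to the imputed set but no last score. The tipping-point analysis needs p below 0.10 and more than 5% missing, so a promising result with p between 0.10 and 0.20 never triggers it.

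**Conclusion.** The omission is certain from the covariate list and the model statement. It applies to subjects without a good discharge, last assessed after baseline and before Day 8, who share arm, listed covariates and last day. Its effect on the trial result is not known, because the documents give no missing-data rate.

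The figures of 1.06 (3% missing) and 1.11 (5% missing) are upper bounds conditional on assumed transitions and fully arm-differential loss. They are not estimates, and other assumed transitions move them, as the range in the working shows. With similar losses in the two arms the bias is much smaller.

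Two stronger readings are tempting. One is that the primary odds ratio is biased: that needs status at loss to differ by arm, which nothing in the documents shows. The other is that every ventilated and every room-air dropout is treated alike: a subject discharged home is set to 2 in the primary analysis and is not imputed. The point is a worthwhile improvement to the primary model, not a flaw that invalidates it.

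**What to change.** Add the ordinal score on day j (ordscore_j) for all subjects to the VAR and MONOTONE LOGISTIC statements of each day-j model, as is already done for discharge status.

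- Collapse sparse levels, for example 3–4, 5, 6 and 7.
- Let goodischstat_j represent subjects discharged home by day j; give them one fixed level of ordscore_j so that the variable is never missing.
- Exclude completers already dead on day j from the fit. Their Day 8 score is always 8, which would cause separation.
- Give subjects in long-term acute care, hospice or another hospital their last recorded score.
- For j = 1 the new variable repeats the baseline score and can be left out.

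The cost is a few more parameters in a model that already carries nine covariates for about 200 subjects, and some collapsing of levels. Daily scores stop at discharge, so the coding rules must be written down. Sample size, estimand and data collection do not change.

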5. SAMPLE SIZE CONSIDERATIONS

We have chosen a sample size of 100 per arm for the proof of concept stages. The power can be computed for the Study Day 8 ordinal score on the basis of an odds ratio representing clinical improvement. The odds ratio represents the odds of improvement in the ordinal scale for treatment relative to placebo. The sample size to detect a given odds ratio for 1:1 randomization using a 2-tailed test at level α is given by

$$\frac{12(z_{\alpha/2} + z_{\beta})^2}{\lambda^2(1 - \sum_{i=1}^K p_i^3)}$$

where λ is the log odds ratio, p_i is the overall probability (combined over both arms) of being in the i^{th} category of the K ordinal outcomes, $z_{\alpha/2}$ and z_{β} are the $1 - \alpha/2$ and $1 - \beta$ quantiles, respectively, of the standard normal distribution.

However, to fully understand all aspects of the testing procedure, we have simulated the probabilities of an intervention: a) being declared futile after 50 subjects per arm, b) being declared efficacious after 50 subjects per arm, and c) being declared promising by 100 subjects per arm.

The interim analysis will find an intervention futile if its point estimate for the primary endpoint has an odds ratio <1 . An intervention can be declared efficacious early after 50 subjects per arm if two-sided $p < 0.001$ and $OR > 1$. If the intervention continues to 100 subjects, it will be declared promising if the final p -value is < 0.20 and $OR > 1$, and statistically significant if the final p -value is < 0.05 . More details are provided in Interim Analysis Section.

Table 4 displays the outcome probabilities in the control arm for sample size determination; this uses preliminary unpublished data from the remdesivir arm in ACTT study. The categories of the 8-point ordinal scale are described in Section 3.2.

Table 4: Expected distribution of ordinal outcomes for the control arm at Study Day 8

Severity Outcome	Outcome (%)
1. Not hospitalized, no new or increased limitations on activities	0.0
2. Not hospitalized, but new or increased limitation on activities and/or requiring new or increased home oxygen, CPAP or BiPAP	34.6
3. Hospitalized, not requiring new or increased supplemental oxygen - no longer requires ongoing medical care	1.2
4. Hospitalized, not requiring new or increased supplemental oxygen - requiring ongoing medical care (COVID-19 related or otherwise)	10.6
5. Hospitalized, requiring new or increased supplemental oxygen	17.1

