6. GENERAL STATISTICAL CONSIDERATIONS

6.1. General Principles

This is a proof of concept double-blind placebo controlled randomized trial testing a superiority hypothesis where interventions with a two-sided p-value $< .20$ will be declared promising and will be considered statistically significant if the final two-sided p-value is $< .05$. These data will be summarized by treatment (intervention name versus placebo) and when appropriate by baseline ordinal score. Additionally, data will be described according to the appropriate summary statistics, e.g.

- Percentages/proportions/odds ratios for categorical data. For tabular summaries of percentages/proportions, the denominator (e.g., number of subjects in the specified population) will be displayed.
- Means, standard deviation, median, and/or range for continuous data, median and confidence intervals for time-to-event data.

Confidence intervals will be generated; 95% and 80% confidence intervals will be generated for primary and key secondary outcomes. For hazard ratio and odds ratio estimates, Wald confidence intervals will be used. For confidence intervals of proportions for other efficacy and safety outcomes, Blaker confidence intervals will be used.

In general, all tables will have corresponding listings of data presented unless noted otherwise.

When calculating treatment effects (e.g., differences, hazard ratios, odds ratios) from regression modelling, placebo will be used as the reference group. Subjects on interventions will only be compared to control subjects who could potentially have been randomized to that intervention (i.e., they met eligibility criteria for the intervention and are at a site where the intervention was enrolling at the time of the subject's randomization). Analyses of newly added arm(s) will be performed comparing concurrently enrolled control subjects. For any modeling that uses covariates defined in Section 6.4, the category listed last for each variable in that section will be used as the control group for the interaction analysis and covariate-adjusted analyses.

For the time-to-event analyses, the following SAS pseudocode will be used to generate stratum-specific median time to event estimates and confidence intervals and stratum-specific Kaplan-Meier curves.

```
proc lifetest data=dataset plots=(s);
  time timevariable * censorvariable(1);
  test treatmentvariable;
run;
```

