  ods output oddsratioswald = orest parameterestimates=pars;
run;
```

```
*Keep only estimates for the treatment variable;
```

```
data pars1;set pars;where Variable='Treatment variable';run;
```

```
*Combine estimates;
```

```
PROC MIANALYZE DATA=pars1;
  ODS OUTPUT PARAMETERESTIMATES= logor;
  MODELEFFECTS estimate ;
  STDERR stderr ;
```

```
RUN;
```

```
*Transform estimates from the log(OR) scale to the OR scale;
```

```
data OR;
  SET logor;
  OR_estimate = EXP(ESTIMATE);
  OR_LCL_95 =OR_estimate*EXP(-1.96*STDERR);
  OR_UCL_95 =OR_estimate*EXP(+1.96*STDERR);
  OR_LCL_80 =OR_estimate*EXP(-1.28*STDERR);
  OR_UCL_80 =OR_estimate*EXP(+1.28*STDERR);
```

```
RUN;
```

Similar pseudocode for odds ratio between the binary progression strata will use used for the Day 8 ordinal score endpoint analyzed by proportional odds using multiple imputation.

If the primary analysis results are at least borderline significant with a p-value < 0.10 and more than 5% of subjects have missing primary endpoint data, additional analyses will be performed to evaluate the effect of the missing data assumptions on the results. Using a tipping point strategy, these analyses will vary the Day 8 ordinal score independently across groups to determine if there is a distribution of missing data that would result in a change of conclusion.

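### When more than 5% of Day 8 scores are missing, promising calls with p from 0.10 to 0.20 get two alternative imputations but no tipping-point analysis

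*SAP*

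**What the plan says.** SAP 6.1 states the decision rule: "interventions with a two-sided p-value $< .20$ will be declared promising". SAP 5 applies it at full enrolment ("If the intervention continues to 100 subjects, it will be declared promising if the final" p-value is below 0.20 and the odds ratio exceeds 1). Both sections keep p below 0.05 as a separate label, statistically significant.

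SAP 6.5.2 makes the tipping-point analysis conditional on two things together, a primary p-value below 0.10 and a missing Day 8 score in more than one subject in twenty: "If the primary analysis results are at least borderline significant with a p-value < 0.10 and more than 5% of subjects have missing". Once both parts of that condition are met, "Using a tipping point strategy, these analyses will vary the Day 8 ordinal score independently across groups", looking for a distribution of missing scores that would change the conclusion. The SAP does not say which threshold defines that change.

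Two other treatments of missing Day 8 scores do not depend on the p-value (SAP 6.5.1, Table 7; rows of Table 16). Sensitivity Imputation 1 uses multiple imputation for everyone with data missing after the last assessment. Sensitivity Imputation 2 uses the complete-data rules, ending in last observation carried forward.

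**The concern.** The trigger is tied to a level that is not the trial's decision level. No section of the SAP uses 0.10 to decide anything, and none extends the tipping-point analysis to p from 0.10 to 0.20. For a result in that band the conclusion under the plan is promising, and the one analysis designed to ask whether missing data could overturn a conclusion is not run.

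The stake is the go decision. SAP 4.1 says the general aim is not clear statistical significance but to choose products for larger studies. A call just inside 0.20 can send an arm forward, and it has the least margin against unfavourable missing scores.

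**Working it through.** **Inputs.** 100 per arm, 1:1 (SAP 5). Control Day 8 distribution from Table 4, categories 1 to 8: 0.0, 34.6, 1.2, 10.6, 17.1, 8.8, 24.2, 3.5%. Interim at 50 per arm, arm dropped if the estimated odds ratio is below 1 (SAP 5, 6.2.1). Promising at p < 0.20; trigger at p < 0.10.

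**Step 1: reproduce the plan's power at odds ratio 2 by formula.** Each control cumulative probability c becomes OR·c/(1 − c + OR·c) in the active arm. Category 2, for example, becomes 2(0.346)/(0.654 + 0.692) = 0.514. Averaging the arms gives Σp³ = 0.092. The SAP 5 sample-size formula, solved for power with N = 200, is

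Φ(λ·√[N(1 − Σp³)/12] − z), where λ = ln 2 = 0.693.

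The first term is 0.693 × √(200 × 0.908/12) = 2.696. Then:
- α = 0.05: Φ(2.696 − 1.960) = 0.769 (Table 5: 0.765)
- α = 0.10: Φ(2.696 − 1.645) = 0.853
- α = 0.20: Φ(2.696 − 1.282) = 0.921 (Table 5: 0.913)

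Table 5 is slightly lower, as the SAP says it should be because of the futility look. Without that look, the share of favourable p < 0.20 results that fall in 0.10–0.20 is (0.921 − 0.853)/0.921 = 7%.

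**Step 2: simulate with the futility look.** 200,000 trials per odds ratio, multinomial outcomes, unadjusted proportional-odds score (Wilcoxon) test at both looks. Interim efficacy crossings are left in, which is the variant that matches Table 5. The exempt share is [P(p < 0.20) − P(p < 0.10)] / P(p < 0.20), in the favourable direction.

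| True OR | Table 5, α = .20 | Simulated p < 0.20 | Simulated p < 0.10 | Difference (share of all trials) | Share of promising calls |
|---|---|---|---|---|---|
| 1.00 | 0.096 | 0.095 | 0.049 | 0.046 | 49% |
| 1.25 | 0.329 | 0.332 | 0.219 | 0.113 | 34% |
| 1.50 | 0.604 | 0.603 | 0.471 | 0.132 | 22% |
| 2.00 | 0.913 | 0.909 | 0.843 | 0.066 | 7% |

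The last column uses unrounded values. Table 5 is matched to within 0.004 in every row.

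**Step 3: are the exempt calls the fragile ones?** The documents give no missing rate, so this step assumes 12 of 200 missing (6%, just over the gate), 6 per arm. The 6 active-arm scores are made worse and the control scores left alone. Over true odds ratios 1 to 2, the share of calls that lose promising status is:

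| Missing active-arm scores | p 0.10–0.20 | p < 0.10 |
|---|---|---|
| One category worse | 64–67% | 0.0% |
| Two categories worse | 94–96% | 0.5–2.7% |

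Judged against the promising rule, the trigger runs the search where modest departures almost never matter and omits it where they usually do.

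**The case against.** **The 5% gate.** The percentages in Step 2 classify calls by p-value only. A call loses a tipping-point analysis only if more than 5% of Day 8 scores are also missing. SAP 6.5.1 expects small amounts of missing data, plans chart review, and assigns a score of 8 after death and 2 after a good discharge before any multiple imputation. At 5% or less, no result gets the analysis and moving the p threshold changes nothing. This stands, and it limits the reach of the point.

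**Other checks exist.** A reader might infer that calls between 0.10 and 0.20 go without any missing-data check. The documents do not support that: Sensitivity Imputations 1 and 2 run at every p-value, and a blinded committee may adjudicate unclear Day 8 scores. They are not substitutes, though. The first draws from the same covariate model and the second is one fixed scenario; neither varies scores separately by arm or searches for a reversal.

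**The 49% needs context.** It applies to a drug with no effect and is about 5% of such trials. Those calls arise by chance in complete simulated data, so a tipping-point analysis would show them to be fragile, not false.

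**The trigger may be deliberate.** Borderline significance fits the separate 0.05 label, so the text does not contradict itself. This is weak, because promising is the label that carries the decision. A stage-specific SAP may also change missing-data handling; none is among the documents reviewed.

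**Conclusion.** The point holds within limits. If more than 5% of Day 8 scores are missing, promising calls with p from 0.10 to 0.20 get the two alternative imputations but not the tipping-point analysis. By p-value alone they are 49%, 34%, 22% and 7% of promising calls at true odds ratios 1.0, 1.25, 1.5 and 2.0, or about 5%, 11%, 13% and 6 to 7% of all trials.

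A reader might infer that a large part of all positive calls escapes the check. That goes too far: it depends on an unstated missing rate, and at an odds ratio of 2, the large effect SAP 4.2 gives as its example, the share is only 7%.

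The shares rest on an unadjusted test with no missing data; the planned covariate-adjusted model with multiple imputation could shift them slightly. The fragility figures rest on the assumed 6% missing. The primary test, the promising rule and Table 5 are unaffected. This is a cheap improvement.

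**What to change.** In SAP 6.5.2, replace the p-value part of the trigger so that it reads: *two-sided p < 0.20 and more than 5% of subjects have missing primary endpoint data.*

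Add no direction condition. The present trigger has none, so requiring an odds ratio above 1 would remove the analysis for unfavourable results that p < 0.10 now covers. It would also be ambiguous: SAP 5 defines the odds ratio as odds of improvement, whereas Table 16 is titled for inferior clinical status.

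Define a change of conclusion as p moving to 0.20 or above and, where the result was declared statistically significant, also as p moving to 0.05 or above.

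With this wording no promising call is excluded by its p-value. The chance of meeting the p-value part in the favourable direction rises from 0.049 to 0.095 at a true odds ratio of 1.0 and from 0.843 to 0.909 at 2.0. The cost is an occasional extra programmed analysis; sample size and the primary analysis stay as they are.
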